5.3.2 Variables

5.3.2.1 Variables to determine the primary objective

- Rate of major malformations (as defined in section 5.3.1.) in fetus and newborn

- Prescribed treatment in first trimester for each indication
- Indication of use
- Risk factors and potential confounders as per section 5.3.2.4.

5.3.2.2 Variables to determine the secondary objective

- Rate of other malformations in fetus and newborn
- Progestogen intake in first trimester for each indication
- Indication of use
- Baseline information
 - Age
 - BMI
 - Race
 - Region of residence
 - Socioeconomic status (SES)
 - Other (cf. section 5.3.2.4.)
- Pregnancy outcome
- Newborn health e.g. NICU admission, prematurity, weight/height newborn at delivery
- Maternal health during pregnancy e.g., obstetric disease, lifestyle (smoking and alcohol), infection, pregnancy-related complication

5.3.2.3 Other variables

Further variables, including known risk and potential confounding factors, for malformations will be collected at baseline and during follow-up. Examples include family and personal history of malformations, vitamin and folic acid intake, infections, previous pregnancy history, environmental exposure, obstetric disease, and medical treatment, IVF/ART insertion technique (if applicable) etc. A detailed overview of all variables is shown in section 5.3.2.4.

5.3.2.4 Variables collected per timepoint

Variables	Baseline	FU1 At week 24	FU2 6-12 weeks after EDD
Filled by	Participant (ePRO)	Participant (ePRO)	Participant (ePRO)
Study eligibility status (based on inclusion and exclusion criteria)	Assessed by recruiting physician & via participant screening form in EDC system by study participant	NA	NA
Informed Consent	x	NA	NA
Select indication for study inclusion (cohort A or B)	x		
Demographic and social characteristics			
Body weight (in Kg) before current pregnancy	x		
Current body weight		x	x

Variables	Baseline	FU1 At week 24	FU2 6-12 weeks after EDD
Filled by	Participant (ePRO)	Participant (ePRO)	Participant (ePRO)
Height (in cm)	x		
Birth year	x		
Race	x		
Region of residence (rural, urban)	x		
Education	x		
Monthly household income	x		
Pregnancy/Reproductive History			
Week since last menstrual period	x	x (only for IVF/ART group not being pregnant at study start)	
Time to pregnancy since pregnancy wish	x	x (only for IVF/ART group not being pregnant at study start)	
Previous Pregnancy/-ies and outcome	x		
Including previous malformations	x		
Treatment			
Study treatment for indication	x	x	
Treatment start	x		
Treatment duration	x		
Fertility treatment for current pregnancy	x		
Medical History			
Existing obstetric disease & treatment	x		
Pregnancy-related/new obstetric disease & treatment		x	x
Infections during pregnancy	x	x	x
COVID-19 vaccination	x	x	x
Environmental Exposure			
Vitamin intake	x	x	
Folic acid intake	x	x	
Environmental exposure	x	x	x
Family History			
Family history malformations	x		
Personal history malformations	x		
Consanguinity	x		
Lifestyle			

Variables	Baseline	FU1 At week 24	FU2 6-12 weeks after EDD
Filled by	Participant (ePRO)	Participant (ePRO)	Participant (ePRO)
Smoking	x	x	x
Alcohol consumption	x	x	x
Study outcome parameters			
Current pregnancy status		x	x
Outcome pregnancy		x	x
Reason for end of pregnancy (if applicable)		x	x
Date of pregnancy end (if applicable)		x	x
Malformations identified in fetus/newborn		x	x
Date of diagnosed malformation (if applicable)		x	x
Diagnostic test identifying the malformation (if applicable)		x	x
Date of delivery			x
Weight newborn at birth			x
Height newborn at birth			x
Sex of the fetus/newborn		x	x

5.4 Data sources

Eligible study participants will be asked to complete study registration by giving their consent to study participation, and providing their contact details required for follow-up. Following their consent, study participants will be asked to complete a questionnaire at baseline visit using the ePRO solution by MediData [9]. The baseline questionnaire will cover basic demographic and gynecological history and a detailed review of obstetric history and risk factors for major malformations. In addition, study participants will be sent two follow-up questionnaires coinciding to the following timepoints – approximately at 24 weeks of gestation and 6 to 12 weeks after the initial EDD. All questionnaires will be completed by the study participant directly via the ePRO questionnaire in Medidata. Direct follow-up (i.e., active surveillance) with study participants enables the collection of comprehensive information on outcomes of interest, regardless of whether they were diagnosed and treated by the HCP.

Follow-up data to be collected from the study participants (ePRO) will describe the clinical status of the pregnancy, potential malformations and change in risk factors as described in section 5.3.2.4 Variables collected per timepoint.

During the informed consent process, study participants are asked to provide the name and address of the diagnosing/treating HCP who is involved in their obstetric care. In case a primary outcome of interest, i.e., a major malformation is reported by the study participant, the reported event will be confirmed via review of medical documentation. Medical documentation can be provided by either the study participant, or by the diagnosing/treating HCP. ZEG Berlin will contact the relevant HCP and inform him/her about the study objectives and will share the subject's informed consent to access the medical information. Follow up by ZEG

Berlin will include obtaining hospital records and/or discharge summaries either via the study participant or diagnosing/treating HCP.

5.5 Study size

Two independent cohorts will be considered in the analysis: (A) study participants with bleeding in early pregnancy and/or recurrent pregnancy loss and (B) study participants receiving IVF / ART. Sample size calculations for both cohorts are similar as based on an incidence proportion of major malformation at birth of 200 per 10,000 births for both indications [10–14]. It is expected that dydrogesterone is associated with a risk of major malformation that is not higher than the risk associated with non-use of dydrogesterone. The study is powered to test the non-inferiority of dydrogesterone treatment.

Assuming a drop-out rate of 20% and a rate of major malformation in fetal newborn of 0.02, sample size calculations show that approximately 5,500 study participants per cohort are statistically sufficient (power = 90%, one-sided $\alpha = 0.025$) to exclude a 2.0-fold risk (Odds Ratio) in the dydrogesterone cohort. The test statistic used is the one-sided Score test [15].

Table 1 and Table 2 show proposed sample sizes for sub-group specific allocation rates.

Cohort A: bleeding in early pregnancy / recurrent pregnancy loss

Table 1: Group allocation: 30% (dydrogesterone) versus 70% (reference)

Endpoint	Incidence proportion		Non-inferiority OR	Effective sample size		20%-Drop-out inflated sample size	
	Reference	DYD		Reference N ₁	DYD N ₂	Reference N ₁	DYD N ₂
Major malformation	0.02	0.02	2.0	3,136	1,343	3,920	1,679

Cohort B: IVF/ART

Table 2: Group allocation: 50% (dydrogesterone) versus 50% (reference)

Endpoint	Incidence proportion		Non-inferiority OR	Effective sample size		20%-Drop-out inflated sample size	
	Reference	DYD		Reference N ₁	DYD N ₂	Reference N ₁	DYD N ₂
Major malformation	0.02	0.02	2.0	2,059	2,059	2,574	2,574

The total number of study participants will be 11,000 across all geographical study sites China, Turkey and Russia.

Sample size has been calculated using the Statistical Software PASS 2021 Power Analysis & Sample Size [16].

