The primary variable of interest is the rate of major malformations in fetus and newborns. Data are collected on treatment, treatment indication, risk factors and potential confounding factors for malformations.

Data sources

Study data, information on risk factors and potential confounding factors, and information on malformations will be obtained from the study participants directly via ePRO. In case a potential major malformation is reported by the study participant, the reported event will be confirmed via review of medical documentation provided by the study participant or alternatively, obtained via the treating HCP.

Study size

Approximately 11,000 study participants (5,500 early pregnancy bleeding/recurrent pregnancy loss and 5,500 IVF/ART) will be recruited via a network of recruiting HCPs prescribing dydrogesterone or other treatment. Approximately 5,500 study participants per subcohort are statistically sufficient (assumptions: power = 90%, one-sided $\alpha = 0.025$, 20% drop-out rate, incidence proportion of 200 major malformations per 10,000 births) to exclude a 2.0-fold risk (Odds Ratio (OR)). The study is powered to test the non-inferiority of dydrogesterone treatment.

Data analysis

The primary analysis will focus on an “as treated” (AT) population analysis set whereby the outcomes of interest are assigned to the treatment exposure during the first trimester of pregnancy. The risk of major malformations will be assessed by unconditional logistic regression for each indication. Potential confounding or risk factors will be considered either in a pre-analysis step regarding cohort balancing using methods such as propensity scores, or by subsequent inclusion into the logistic model as cofactors for adjustment of the treatment effect. Crude and adjusted ORs and 95% confidence intervals (CI) will be estimated. The null hypothesis to be tested is: $(OR_{MM}) \geq 2.0$ (i.e., the malformation odds ratio for dydrogesterone vs. non-dydrogesterone is higher or equal to 2.0). The alternative hypothesis is defined as $OR_{MM} < 2.0$.

1 Amendments and updates

Number	Date	Section of study protocol	Amendment or update	Reason
V01-00	16-JUL-2021	NA	First version	
V02-00	11-OCT-2021	
 Section 3: Rationale and background Section 5.2.2.1 Inclusion criteria Section 5.7.3 Interim analyses 	Amendments as per recommendation by the Global Ethics Committee	

2 Milestones

Milestone	Planned date

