Global Ethics Approval	September 2021
Registration in the EU PAS register	October 2021
Start of data collection (First Patient In)	December 2021
End of data collection (Last Patient Last Follow-Up)	April 2024
Study interim/progress report 1	March 2022
Study interim/progress report 2	December 2022
Study interim/progress report 3	September 2023
Data base lock	August 2024
Final report of study results	November 2024

3 Rationale and background

Progestogens are commonly prescribed to women for the indication of luteal phase support (LPS) during IVF (in vitro fertilization)/ART (assisted reproductive technology) treatment, when presenting with early pregnancy bleeding or recurrent pregnancy loss. While miscarriage is a frequent complication of early pregnancy (estimated to occur in 10–20% of pregnancies), recurrent miscarriage is less common, with prevalence estimates varying between 0.8% recurrent miscarriage is less common, with prevalence estimates varying between 0.8% and 3% [1]. Recommendations for treatment options for miscarriage differ between guidelines, largely a result of the guidelines being continually updated in line with the latest clinical evidence. In practice,

the onus is on the prescribing physician to ensure their practices are based on the most recently available data and local recommendations. After 60 years of availability on the market, the available clinical and post-marketing safety data have indicated that dydrogesterone has a favorable benefit-risk profile in the approved indications. However, recent implications and isolated claims by individuals within the scientific community [2–5] have raised some questions related to the safety of dydrogesterone, including a retrospective cohort study suggested an increased risk of major cardiac malformations in newborns exposed to dydrogesterone [3]. The study was methodologically flawed and has since been retracted by the publishing journal.

This registry study aims to establish a scientifically sound pregnancy and newborn safety data set to document any putative teratogenic risks upon exposure to progestogens. A large sample size registry with detailed characterization of participants' background, treatment and pregnancy outcome will provide generalizability and precision in addition to possible future regulatory requests from health authorities.

4 Research question and objectives

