5.2.2.3 Withdrawal / drop-out / lost to follow-up (LTFU)

Study participants can refuse to further participate, or may withdraw from the study, at any time and without giving a reason. As this is an observational study, withdrawal from the study is independent of the underlying therapy and will not affect medical care.

If a study participant wishes to terminate study participation, no further data will be collected. Data which were collected prior to withdrawal may be used in the data analysis for the purpose of this study. In case a study participant would like to withdraw the consent given earlier, the withdrawal should be documented in the electronic Case Report Form (eCRF) in the EDC solution by MediData. Study participants who withdraw from the study prior to regular study end will be included in drop-out numbers.

Study participants who experience a spontaneous abortion or pregnancy termination during study conduct will not receive further follow-up (FU) questionnaires. These study participants are considered to have reached regular end of study (REOS) after completion of the follow-up questionnaire in which the spontaneous abortion or pregnancy termination was reported.

A study participant becomes lost-to-follow-up (LTFU) when the study questionnaire(s) are no longer completed and re-contact attempts remain unsuccessful. To limit LTFU, ZEG Berlin will implement a well-established active-surveillance (AS) methodology. Automatic reminders (e.g., e-mail) to complete study questionnaires will be issued via the ePRO solution by MediData. In case of ongoing non-response, further manual contact attempts (e.g., telephone) will be initiated by the local field organizations team.

Participants will not be replaced after drop-out or LTFU.

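### The stated 90% power per cohort does not follow from the protocol's own inputs: it is about 87% in cohort A and about 89% in cohort B, before any allowance for miscarriage

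*Protocol*

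**What the plan says.** Section 5.5 plans two cohorts of about 5,500 and states that "sample size calculations show that approximately 5,500 study participants per cohort are statistically sufficient (power = 90"%). The level attached to this figure is 0.025, one-sided, and the risk to be ruled out is an odds ratio of 2.0. The abstract makes the same claim. The test is a one-sided score test, and the null hypothesis in the abstract and section 5.7.2 is that "the malformation odds ratio for dydrogesterone vs. non-dydrogesterone is higher or equal to 2.0".

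The rate and the allowance for loss are given together: "Assuming a drop-out rate of 20% and a rate of major malformation in fetal newborn of 0.02". The rate is an "incidence proportion of major malformation at birth of 200 per 10,000 births for both indications".

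- Cohort A, "Table 1: Group allocation: 30% (dydrogesterone) versus 70% (reference"): effective sizes 1,343 (dydrogesterone) and 3,136 (reference), inflated to 1,679 and 3,920.
- Cohort B, equal allocation: 2,059 per group, inflated to 2,574 per group.

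Section 5.2.2.3 counts withdrawal before regular study end as drop-out. On women with a spontaneous abortion or termination it says: "These study participants are considered to have reached regular end of study (REOS) after completion of the follow-up questionnaire" in which the event was reported. Section 3 describes miscarriage in general as "estimated to occur in 10–20% of pregnancies". Section 5.7.2 calculates overall incidence over all observed pregnancies in a cohort.

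**The concern.** Every input to the power calculation is stated, so the 90% can be checked, and it does not come out. Table 1 also inflates to more women than cohort A is planned to enrol. In addition, a rate per birth is applied to enrolled pregnancies with drop-out as the only deduction, in a study where one cohort is defined by bleeding or recurrent loss.

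The stated power concerns the primary hypothesis of a safety study meant to exclude a doubling of major malformations. Anyone relying on 90% would overrate the chance of showing non-inferiority, mainly in cohort A, and could read too much into a result there that fails to exclude 2.0.

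**Working it through.** **Inputs (section 5.5, abstract, section 5.7.2).** True rate 0.02 in both groups; margin OR 2.0; one-sided alpha 0.025 (z = 1.960); score test; allocation 30:70 (A) and 50:50 (B); drop-out 20%.

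**1. The plan's own figures.** The drop-out inflation is right:

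- 3,136/0.8 = 3,920; 1,343/0.8 = 1,679; 2,059/0.8 = 2,574.
- Totals: 5,599 (A) and 5,148 (B), together 10,747.

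The effective sizes (4,479 and 4,118) could not be reproduced. No single formula tried gave both: odds-ratio score, Wald log-odds-ratio, likelihood ratio, arcsine, risk-difference and risk-ratio forms. A null-variance score formula for a *risk ratio* of 2.0 gives 4,119, close to Table 2, but the same formula needs 4,873 for Table 1, not 4,479.

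**2. Power at the tabulated sizes.** Let x be the events among nD dydrogesterone women. Let pD and pR be the rates fitted under OR = 2 with the total number of events held fixed. Then

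Z = (x − nD·pD) / √V, with V = 1 / [1/(nD·pD(1−pD)) + 1/(nR·pR(1−pR))],

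and non-inferiority is shown if Z ≤ −1.960.

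Table 1 at expected counts:

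- x = 1,343 × 0.02 = 26.86; pD = 0.03052, pR = 0.01550; nD·pD = 40.99.
- 1/V = 1/39.74 + 1/47.84 = 0.0461, so √V = 4.66.
- Z = (26.86 − 40.99)/4.66 = −3.03.
- Using the null variance, power = Φ(3.03 − 1.96) = Φ(1.07) = 85.8%. A power of 90% would need 1.960 + 1.282 = 3.24.

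Table 2 in the same way: pD = 0.02655, pR = 0.01345, Z = −3.17, power = Φ(1.21) = 88.7%.

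These are approximations. The exact figure sums the two binomial distributions over the rejection region of the same test.

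**3. Power at the planned 5,500.** 5,500 × 0.8 = 4,400 evaluable: 1,320/3,080 (A) and 2,200/2,200 (B).

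| Odds-ratio score test, 2% v 2% | Table 1 sizes | Table 2 sizes | A, 4,400 | B, 4,400 |
|---|---|---|---|---|
| Normal approximation, null and alternative variances | 86.5% | 86.3% | 85.9% | 88.3% |
| Normal approximation, null variance only | 85.8% | 88.7% | 85.2% | 90.7% |
| Exact | 87.3% | 87.1% | 86.9% | 89.0% |

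A Wald log-odds-ratio approximation gives 84.5% and 87.6% at the tabulated sizes.

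By exact calculation, 90% needs about 4,890 evaluable pregnancies in A and 4,560 in B. The 99 women between 5,599 and 5,500 are 1.8% of Table 1's total, and they move exact power in A from 87.3% to 86.9%.

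**4. Early losses.** The protocol gives no miscarriage rate after enrolment. As an assumption, take its general 10-20% and apply it on top of the full 20% drop-out. Two treatments of these women are possible:

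- *Removed:* 4,400 × 0.9 = 3,960 or 4,400 × 0.8 = 3,520 remain, at a 2% rate.
- *Kept in the denominator with no malformation detected:* 4,400 remain, and the rate falls to 0.02 × 0.9 = 0.018 or 0.02 × 0.8 = 0.016.

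| Exact power | A, 10% | A, 20% | B, 10% | B, 20% |
|---|---|---|---|---|
| Removed | 82.5% | 77.9% | 85.7% | 81.4% |
| Kept, rate diluted | 83.2% | 78.8% | 85.8% | 81.7% |

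**The case against.** **Cohort B is nearly right.** It is planned at 5,500, above the 5,148 its table requires, and one approximation puts it at 90.7%. This stands. A reader might infer that neither cohort comes near 90%; before early losses the documents support that only for cohort A.

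**The 5,599 gap is trivial.** The text says approximately 5,500, the cost is under half a power point, and the two tables sum to less than 11,000. This also stands. It is an inconsistency to tidy up and does not cause the shortfall.

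**The miscarriage figures are assumed.** The 10-20% describes pregnancies in general. Enrolment requires a positive test and, in most routes, evidence of an intrauterine pregnancy, so the rate after enrolment could be lower; in women with bleeding or recurrent loss it could be higher. Section 5.9 expects very little loss to follow-up, so the 20% may contain headroom: 10% drop-out plus 10% miscarriage leaves 0.9 × 0.9 = 81%, or 4,455 women, with exact power 87.2% (A) and 89.4% (B). A termination for a fetal malformation can itself be a primary event, because fetal malformations are in the outcome and are asked about at the first follow-up. All of this is fair. A reader might take 78% or 81% as the true power of the study; the documents do not support that. They support only that no allowance is stated.

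**The 2% is itself uncertain.** At 2.25%, exact power with 4,400 evaluable is 90.3% (A) and 92.1% (B); at 1.8% it is 83.2% and 85.8%. This limits the practical weight of the point. It does not rescue the sentence, which claims 90% at 2%.

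A reader might also add a loss from propensity weighting. Section 5.7.2 leaves the choice between weighting and covariate adjustment open and gives no basis for a figure, so none is used here.

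**Conclusion.** The 90% claim is wrong as written. On the stated inputs the shortfall at 5,500 is about 3 points in cohort A (3 to 5 across odds-ratio score versions) and about 1 point in cohort B, where it is within reach of the choice of approximation. This rests only on section 5.5 and needs no outside assumption. What produced the tabulated sizes cannot be determined without the software output.

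The missing allowance for miscarriage and termination is a separate and real gap: the rate is per birth, the deduction is for drop-out only, and these women are neither births nor drop-outs. Power falls whichever way they are counted. The amount, down to about 78-83% (A) and 81-86% (B), depends on the assumed 10-20% stacked on a full 20% drop-out, and is a sensitivity range only.

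The margin, the test and the validity of the analysis are not affected. What needs correcting is the statement of what the design can deliver.

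**What to change.** Keep 11,000 participants.

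- Rerun the sample-size calculation for the odds-ratio score test, file the output, and correct Tables 1 and 2.
- In the abstract and section 5.5, restate power as about 87% (cohort A) and 89% (cohort B) for 4,400 evaluable pregnancies per cohort.
- Reconcile Table 1's 5,599 with the planned 5,500 and withdraw the statement that 5,500 suffices for 90% in cohort A.
- State how miscarriages and terminations count in the denominator, so that it agrees with the per-birth rate in section 5.5 and with the all-pregnancies denominator in section 5.7.2.
- Give power after early losses as a labelled sensitivity range, with its assumed rates, and not as the power of the study.

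The cost is one recalculation and some wording. The stated power becomes slightly less favourable; no participants are added and the design does not change.

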5.6 Data management

5.6.1 Databases

During the study, two different types of data will be collected: (I) administrative data, which includes contact details of HCPs and study participants, and (II) study data, which includes all questionnaire data including baseline data and all subsequent follow-up forms. All study data will be collected and managed through the EDC system, MediData Rave [17] and ePRO [9]. For data security and privacy reasons, administrative data are stored separately from the study data (e.g., firewall). Access to administrative data will be restricted and only be accessible for the teams who require contact with the study participants and/or diagnosing/treating HCPs.

Where local regulations permit, the consent and informed consent form (ICF) signing process will occur electronically via the MediData eConsent application. All outcome variables and potential covariates will be entered in standardized eCRFs. After data entry, missing or implausible data will be queried, and the data will be validated by ZEG Berlin's study data management team.

Study data will be entered directly into the ePRO questionnaire by the study participants via MediData. The quality control of entered data will be supported by edit checks which include range, coding, missing and date checks as well as cross-reference (consistency) checks between variables.

